4.5 TERTIARY/EXPLORATORY ENDPOINT(S) ANALYSIS

4.5.1 Definition of endpoint(s)

The exploratory endpoints are as follows:

- Use of high potency or superpotent TCS rescue medication through Week 24
- Use of systemic immunosuppressant through Week 24, constituting treatment failure
- Change from baseline in Hospital Anxiety and Depression Scale (HADS) total score to Week 24
- Change from baseline in EQ-5D-5L Single Index score to Week 24
- Change from baseline in EQ-5D visual analog scale (VAS) to Week 24
- Change from baseline in skin Pain-NRS to Week 4, Week 8, Week 12, and Week 24, respectively

- Change from baseline in Sleep-NRS to Week 4, Week 8, Week 12, and Week 24, respectively
- Missed school/work days through Week 24
- Incidence of skin-infection TEAEs (excluding herpetic infections) through Week 24
- Proportion of participants who achieve $\geq 75\%$ healed lesions from PAS at Week 4, Week 8, Week 12, and Week 24, respectively
- Change from baseline in exact number of lesions in representative area (as determined from PAS) at Week 4, Week 8, Week 12, and Week 24, respectively
- Change from baseline in Participant Global Impression of Severity (PGIS) of PN to Week 4, Week 8, Week 12, and Week 24 respectively
- Proportion of participants with PGIS score of “none” at Week 4, Week 8, Week 12, and Week 24 respectively
- Proportion of participants with PGIS score of “none” or “mild” at Week 4, Week 8, Week 12, and Week 24 respectively
- Participant Global Impression of Change (PGIC) of PN at Week 4, Week 8, Week 12, and Week 24, respectively
- Proportion of participants with PGIC score of “very much better” at Week 4, Week 8, Week 12, and Week 24 respectively
- Proportion of participants with PGIC score of “very much better” or “moderately better” at Week 4, Week 8, Week 12, and Week 24 respectively.

Hospital anxiety and depression scale (HADS)

The HADS is a PRO instrument for screening anxiety and depression in non-psychiatric populations; repeated administration also provides information about changes to a participant’s emotional state. The HADS consists of 14 items, 7 each for anxiety and depression symptoms; possible scores range from 0 to 21 for each subscale. The following cut-off scores are recommended for both subscales:

- 0 to 7: normal
- 8 to 10: borderline abnormal (borderline case)
- 11 to 21: abnormal.

Euroqol 5 dimensions questionnaire (EQ-5D)

The Euroqol-5 dimensions (EQ-5D) is a standardized PRO measure of health status developed by the EuroQOL Group in order to provide a simple, generic measure of health for clinical and economic appraisal. The EQ-5D consists of 2 parts: the descriptive system and the EQ visual analog scale (VAS). The EQ-5D descriptive system comprises the following 5 dimensions: mobility, self-care, usual activities, pain/discomfort, and anxiety/depression. Each dimension has 5 levels of perceived problems: “no problem”, “slight problems”, “moderate problems”, “severe problems” and “inability to do the activity”. The respondent is asked to indicate his/her health state by ticking (or placing a cross) in the box against the most appropriate statement in each of the 5 dimensions; this results in a 1-digit number expressing the level for that dimension. The digits for 5 dimensions can be combined in a 5-digit number describing the respondent’s health state. The EQ VAS records the respondent’s self-rated health on a vertical VAS where the endpoints are labeled “best imaginable health state (100)” and “worst imaginable health state (0)”. This information can be used as a quantitative measure of health outcome as judged by the individual respondents.

Skin Pain and sleep numeric rating scales (skin Pain-NRS, Sleep-NRS)

Participants will be asked to rate their worst skin pain in the past 24 hours using a 0 to 10 NRS, with 0 = No pain to 10 = Worst pain possible.

In addition, participants will be asked to rate their sleep quality on their past night upon awakening, using a 0 to 10 NRS, with 0 = Worst possible sleep and 10 = Best possible sleep.

Participants will complete the skin pain NRS and sleep quality NRS once a day.

Prurigo activity score (PAS)

The PAS is a clinician-reported outcome (ClinRO) measurement. The original PAS questionnaire Version 0.9 consists of 7 items, developed by expert clinicians in PN.

A 5-item simplified version of the PAS will be used in the current study. Item 4 (exact number of pruriginous lesions in representative area) and Item 5b (percentage of healed prurigo lesions in all pruriginous lesions) will be used for analyses. In addition, Item 2 (number of prurigo lesions) may be used for analysis too.

Participant Global Impression of Change of disease (PGIC) and Participant Global Impression of Severity (PGIS)

The PGIC is a one-item questionnaire that asks participants to provide the overall self-assessment of change in their PN overall on a 7-point scale, compared to just before participant started taking the study injection. Response choices are: 0 = “Very much better”, 1 = “Moderately better”, 2 = “A little better”, 3 = “No change”, 4 = “A little worse”, 5 = “Moderately worse”, 6 = “Very much worse”.

The PGIS is a one-item questionnaire that asks participants to provide the overall self-assessment of their disease severity on a 4-point scale for the past week. Response choices are: 1 = “none”, 2 = “Mild”, 3 = “Moderate”, 4 = “Severe”.

Missed school/work days

Participants who are employed or enrolled in school will be asked to report the number of sick leave/missed school days since the last study assessment.

Photography substudy

Participants in selected sites who decide to participate in this substudy need to provide separate consent. One or several lesions will be photographed at baseline. The same lesions will be photographed at subsequent visits to evaluate their progression.

4.5.2 Main analytical approach

Exploratory efficacy endpoints will be analyzed using the same methodology as secondary efficacy for similar data (continuous or proportion) except the endpoints below.

- Use of high potency or superpotent TCS rescue medication through Week 24
- Use of systemic immunosuppressant through Week 24, constituting treatment failure
- Missed school/work days through Week 24
- Incidence of skin-infection TEAEs (excluding herpetic infections) through Week 24.

The number of participants and percentage with the events for these endpoints will be provided in observed cases. In addition, the time (week) to first event for those participants will also be analyzed using Kaplan-Meier method and the duration of the rescue medication use may be summarized if applicable.

An additional exploratory endpoint of time to first select prohibited/rescue medication that impact efficacy will be provided. This includes medications where WOCF will be applied (see [Table 5](#)).

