Visit	1	2 ^a	3	4	5	6 ^b (EOT)	7 (EOS)	Visit window: ± 3 days for Visits 3, 4, 5, 6, and 7.
DLQI		X	X	X	X	X	X	Entered by participant during site visit on a tablet provided to the site.
HADS		X			X	X	X	
EQ-5D-5L		X			X	X	X	
PGIS	X	X	X	X	X	X		
PGIC			X	X	X	X		
Missed school/work days (baseline version)		X						
Missed school/work days (postbaseline version)					X	X	X	
Modified PAS (screening- baseline version)	X	X						Investigator's assessment to be entered on a tablet provided to the site.
Modified PAS (follow-up version)			X	X	X	X	X	
IGA PN-A and IGA PN-S		X	X	X	X	X	X	
Optional photography (substudy)		X	X	X	X	X	X	

a All assessments at Visit 2 (Day 1) are to be conducted pre-IMP dose with the exception of the assessment of local tolerability of SC injections.

b Participants who discontinue the study treatment prematurely (prior to completing the 24-week treatment period) will perform the EOT assessments at the time of discontinuation to assure a complete clinical assessment in close temporal proximity to the premature termination of study treatment. In addition, to allow assessment of participant outcomes over the stipulated study period, participants will be asked and encouraged to complete all remaining study visits and participate in all assessments according to the visit schedule.

c In case of results showing HBs Ag (negative) and HBc Ab (positive), an HBV DNA testing will be performed and should be confirmed negative prior to randomization. In case of results showing HCV Ab (positive), HCV RNA testing will be performed and should be confirmed negative prior to randomization.

d Assessments/procedures should be conducted in the following order: PRO, investigator assessments, safety and laboratory assessments (including sample collection for ADA, PK, biomarker, and optional DNA and RNA), and administration of IMP.

e Refer to [Section 10.2](#) and central lab manual for collection details.

f PK and ADA samples to be collected prior to the administration of the drug. In the event of any SAE, any AE of severe injection site reaction lasting longer than 24 hours, or any AESI of anaphylactic reaction or systemic allergic reaction that is related to IMP and require treatment, PK and ADA samples will be collected at or near the onset of the event for any additional analysis if required or for archival purposes. Samples for ADA will only be collected for analysis in the event of any SAE for participants from China sites.

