8.1.9 Missed school/work days

Participants who are employed or enrolled in school will be asked to report the number of sick leave/missed school days since the last study assessment.

Participants will complete the questionnaire as described in the SoA (see [Section 1.3](#)). The assessment tool is provided in [Section 10.7.11](#).

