10.7.11 Missed school/work days

Patients with Prurigo Nodularis (PN)

Missed School/Work days BASELINE Visit

Site Number: _____ Patient Study Number: _____

Visit Date (dd/mmm/yyyy): _____ / _____ / _____ Time of Completion: _____ : _____ am/pm

Employment status

1. Have you been working?

- Yes – I am working full time (≥ 4 days/week)
- Yes – I am working part time (< 4 days/week)
- No – I am not working (unemployed, retired)

For those working (full time or part time):

2. How many days have you missed from work because of your Prurigo Nodularis in the last 4 weeks prior to the visit today?

Please do not include time you missed from work for taking part in this research.

Specify: ___ Days

Student status

1. Have you been in school?

- Yes – I am in school full time (≥ 4 days/week)
- Yes – I am in school part time (< 4 days/week)
- No – I am not in school

For those in school (full time or part time):

2. How many days have you missed from school because of your Prurigo Nodularis in the last 4 weeks prior to the visit today?

Please do not include time you missed from school for taking part in this research.

Specify: ___ Days

NOTES:

Please make sure the instructions are read to the patient BEFORE they start the questionnaire.

Assessment periods (i.e., time interval from the date of last assessment through the current date) must be continuous. Leave no gaps. Cumulatively, these periods must cover the entire study duration.

Avoid duplicate reporting. If the patient missed school/work because of his/her PN on the day of

assessment, this day should be recorded only once.

Record only days on which patient's PN prevented him/her to go to school/work. Otherwise, do not record the days on which the patient missed school/work only to participate in study visits.

Print Name (First/Last) of Investigator Completing Assessment Signature Date

R668-XXX-Missed School/work Days Version 1.0 BASELINE; date

Page 1 of 1

Patients with *Prurigo Nodularis (PN)*

Missed School/work days
POST Baseline Visits

Site Number: _____ Patient Study Number: _____

Visit Date (dd/mmm/yyyy): ____ / ____ / ____ Time of Completion: ____ : ____ am/pm

Employment status

1. Have you been working since your last assessment?

- Yes – I am working full time (≥ 4 days/week)
- Yes – I am working part time (< 4 days/week)
- No – I am not working (unemployed, retired)

For those working (full time or part time):

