2. How many days have you missed from work because of your Prurigo Nodularis since the day of your last assessment, including today?

Please do not include time you missed from work for taking part in this research.

Specify: ____ Days

Student status

1. Have you been in school since your last assessment?

- Yes – I am in school full time (≥ 4 days/week)
- Yes – I am in school part time (< 4 days/week)
- No – I am not in school

For those in school (full time or part time):

2. How many days have you missed from school because of your Prurigo Nodularis since the day of your last assessment, including today?

Please do not include time you missed from school for taking part in this research.

Specify: ____ Days

NOTES:

Please make sure the instructions are read to the patient BEFORE they start the questionnaire.

Assessment periods (i.e., time interval from the date of last assessment through the current date) must be continuous. Leave no gaps. Cumulatively, these periods must cover the entire study duration.

Avoid duplicate reporting. If the patient missed school/work because of his/her PN on the day of assessment, this day should be recorded only once.

Record only days on which patient's PN prevented him/her to go to school/work. Otherwise, do not record the days on which the patient missed school/work only to participate in study visits.

Print Name (First/Last) of Investigator Completing Assessment Signature Date

R668-XXX Missed School/work Days Version 2.0; date

Page 1 of 1

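### Missed school/work days are collected as undated counts over about 12 weeks, but SAP 4.5.2 plans n (%) and a Kaplan-Meier time to first event, with no between-arm analysis of the days

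*SAP*

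**What the plan says.** SAP 4.5.1 lists "Missed school/work days through Week 24" among the exploratory endpoints and states who reports it: "Participants who are employed or enrolled in school will be asked to report the number of sick leave/missed school days since the last study assessment". Protocol 8.1.9 agrees.

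The instrument is in Protocol 10.7.11. Each form first asks whether the participant works or is in school, and then asks those who do for a count.

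- Baseline form: "How many days have you missed from work because of your Prurigo Nodularis in the last 4 weeks prior to the visit today".
- Post-baseline form, work: "How many days have you missed from work because of your Prurigo Nodularis since the day of your last assessment, including today".
- Post-baseline form, school: "How many days have you missed from school because of your Prurigo Nodularis since the day of your last assessment, including today".

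No form asks on which dates days were missed. The notes on the form require recall periods without gaps that together span the whole study. The Schedule of Activities (Protocol 1.3) places the post-baseline form at Weeks 12, 24 and 36 only. SAP Table 11 has matching windows: up to Day 126, Days 127 to 210, and after Day 210. If several values fall in one window, the one nearest the target day goes into the by-visit summary.

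SAP 4.5.2 analyses exploratory endpoints by the methods for the secondary endpoints, with four exceptions: topical steroid rescue, systemic immunosuppressant use, missed school/work days, and skin-infection adverse events. For these it gives the number and percentage of participants with the events in observed cases, and "the time (week) to first event for those participants will also be analyzed using Kaplan-Meier method". For missed days it does not say what an event is, when it is taken to occur, or who is in the denominator.

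**The concern.** The template suits the other three exceptions, which come from records with their own dates. Protocol 6.5.1 requires date and time for rescue, Protocol 6.5 requires start and end dates for concomitant medication, and adverse events have onset dates. Missed days are a recalled total with no date attached.

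Two things follow. A Kaplan-Meier curve in weeks needs an event time that the form does not supply, so its shape would come from the visit schedule. And the quantity that the endpoint names, the number of days, has no between-arm analysis in 4.5.2: a participant who missed one day and one who missed sixty contribute the same. This is also the only measure that Protocol 8.9 names under health economics.

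**Working it through.** The plan gives no power, rate or event figure for this endpoint, so there is none to reproduce.

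**1. Recall length.** From the target days in SAP Table 11 (1, 85, 169, 253):

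- (85 - 1)/7 = 12.0 weeks
- (169 - 85)/7 = 12.0 weeks
- (253 - 169)/7 = 12.0 weeks

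An on-schedule participant has two post-baseline forms through Week 24. The first missed day is interval-censored to Weeks 0-12 or Weeks 12-24.

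**2. Effect of dating events to the reporting visit (illustration).** Assume that a proportion p of those at risk miss at least one day by Week 24, at a constant rate, with all forms on schedule.

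- Rate per week: h = -ln(1 - p)/24
- True cumulative incidence at Week 8: 1 - exp(-8h)
- Mean dating delay: 12 - [1/h - 12·exp(-12h)/(1 - exp(-12h))]

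| Assumed p | h | True incidence at Week 8 | Curve at Week 8 | Mean delay (weeks) |
|---|---|---|---|---|
| 20% | 0.0093 | 7.2% | 0 | 6.1 |
| 40% | 0.0213 | 15.7% | 0 | 6.3 |
| 60% | 0.0382 | 26.3% | 0 | 6.5 |

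**3. Any/none against the count (illustration).** Assume 45 workers or students per arm (60% of 75), negative binomial days with dispersion k, and a mean halved on dupilumab. The share with any day is 1 - (k/(k + mean))^k. Power is from 3,000 simulated trials per row at two-sided 0.05, with a z-test on any/none and a Wilcoxon test on the counts.

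| k | Placebo mean days | Any day, placebo / dupilumab | Power, any/none | Power, count |
|---|---|---|---|---|
| 0.3 | 4 | 55% / 46% | 13% | 23% |
| 0.5 | 4 | 67% / 55% | 19% | 38% |
| 1.0 | 4 | 80% / 67% | 33% | 68% |
| 0.3 | 8 | 63% / 55% | 12% | 23% |
| 0.5 | 8 | 76% / 67% | 16% | 40% |
| 1.0 | 8 | 89% / 80% | 22% | 72% |

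The any/none test has the lower power in every row. The sizes depend wholly on the assumed inputs.

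**4. Days lost under the nearest-form rule.** A participant who stops treatment early completes the end-of-treatment assessments then and is asked to keep attending (Protocol 1.3, footnote b). Suppose that form falls on Day 57 and the Week 12 form on Day 85. Both lie in the window ending on Day 126, and the rule keeps Day 85. That form covers only (85 - 57)/7 = 4 weeks, so the (57 - 1)/7 = 8 weeks on the dropped form are lost from the by-visit summary. A total through Week 24 must sum the forms.

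**The case against.** The best defence is one of consequence. The endpoint is exploratory and absent from the hierarchy in SAP 4.6. A by-arm n (%) is a legitimate summary that can show an effect. The SAP never claims to use dates of absence; its time in weeks could mean the reporting week. A count model instead of a percentage is partly a matter of preference. All of that stands and limits the weight of the point. It does not rescue the curve: the SAP does not say that the reporting week is meant, and if it is, the steps still mark visits.

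A reader might also infer more than the documents support:

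- **That non-workers dilute the percentage.** The SAP says observed cases, and the day question is put only to those working or in school, so a non-worker has no observed count. The denominator is unspecified; it is not stated to include them. No employment share is given from which to size a dilution.
- **That the count is never summarised.** The default for continuous data in SAP 4.1 and the windows in Table 11 could permit a descriptive summary of days. Neither promises one for this endpoint, and neither supplies a comparison between arms.
- **That only two event times are possible.** Visits have a ±3-day window, and early end-of-treatment forms can fall at other times. Two intervals is correct only for on-schedule participants.
- **That the move from 4-week to 12-week recall biases the result.** No comparison of any/none with baseline is planned, and both arms have the same scheduled recall. The different lengths are a reason to work with rates, not evidence of bias.
- **That this is the trial's only measure of effect on work.** The DLQI has a work/study item, and its change to Week 24 is in the hierarchy. Missed days is the only count of days lost.

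**Conclusion.** The point holds as a mismatch between instrument and analysis. The form yields undated counts over about 12 weeks from participants who work or study. SAP 4.5.2 plans a time-to-first-event curve that those data cannot support, and it specifies no between-arm analysis of the days. The interval-censoring follows directly from the form and schedule. The 6.1 to 6.5 week delay rests on a constant rate, on-schedule forms and dating to the reporting visit. The power contrast rests on the assumed sample, distribution and effect. Reading the event as any missed day is natural, but the SAP does not define it.

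No confirmatory conclusion depends on this. It is a desirable, low-cost correction to an exploratory table and figure.

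**What to change.** In SAP 4.5.2, before the primary database lock and while blinded:

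1. Remove missed school/work days from the Kaplan-Meier analysis. If timing is of interest, give the proportion with any missed day in each interval (Weeks 0-12 and 12-24).
2. Define the analysis set as participants working or in school during the recall period, as recorded on each form. State how work and school counts combine for someone who does both.
3. Sum days over all forms through Week 24, including an early end-of-treatment form, instead of keeping only the form nearest the target day.
4. Summarise days per unit of recall time by arm and compare the arms, for example by negative binomial regression with log recall time as offset and the 4-week baseline count as covariate. Say what is done for participants with no baseline count because they were not then working or studying.
5. Keep n (%) with any missed day, with workers and students as the stated denominator.

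The cost is SAP wording and one changed table; all data are already collected. The downside is a smaller denominator. Because that group is defined partly by status after randomization, which treatment could influence, a check restricted to those working or studying at baseline would be sensible.

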4.6 MULTIPLICITY ISSUES

The multiplicity procedure is proposed to control the overall type-I error rate for testing the primary and selected secondary endpoints. The overall alpha is 0.05. The comparisons with placebo will be tested based on the hierarchical order below at 2-sided $\alpha = 0.05$:

In US and US reference countries:

- Proportion of participants with improvement (reduction) in WI-NRS by ≥ 4 from baseline to Week 24
- Proportion of participants with IGA PN-S 0 or 1 score at Week 24
- Proportion of participants with both an improvement (reduction) in WI-NRS by ≥ 4 from baseline to Week 24 and an IGA PN-S 0 or 1 score at Week 24
- Percent change from baseline in WI-NRS at Week 24
- Change from baseline in HRQoL, as measured by Dermatology Life Quality Index (DLQI) to Week 24
- Change from baseline in skin Pain-NRS to Week 24
- Change from baseline in Hospital Anxiety and Depression Scale (HADS) total score to Week 24

In all other countries (including EU and EU reference countries, as well as Japan):

- Proportion of participants with improvement (reduction) in WI-NRS by ≥ 4 from baseline to Week 24
- Proportion of participants with IGA PN-S 0 or 1 score at Week 24
- Percent change from baseline in WI-NRS at Week 24
- Change from baseline in HRQoL, as measured by Dermatology Life Quality Index (DLQI) to Week 24
- Change from baseline in skin Pain-NRS to Week 24
- Change from baseline in Hospital Anxiety and Depression Scale (HADS) total score to Week 24.

The study is considered positive when the primary endpoint achieves statistical significance.

